9.5. Events of Clinical Interest

Not applicable.

9.6. Emergency Unblinding of Treatment Assignment

In case of a medical emergency, for a participant's safety management, the procedure for emergency unblinding is provided to the investigator in the IRT Manual. If a participant's treatment assignment is unblinded, the sponsor or its designee should be notified immediately for awareness.

If an investigator, the site personnel performing assessments, or a participant is unblinded, then the participant must discontinue study drug unless there are ethical reasons to have the participant remain on the study treatment. In these cases, the investigator must obtain specific approval from the sponsor's (or its designee's) medical monitor for the participant to continue in the study.

9.7. Pregnancy

Pregnancy, in and of itself, is not regarded as an AE unless there is suspicion that the study drug may have interfered with the effectiveness of a contraceptive medication or method. When a pregnancy has been confirmed in a participant during maternal or paternal exposure to study drug, the following procedures should be followed in order to ensure safety:

- The study drug must be discontinued immediately (female participants only; see Section 7.1 for the maximum permitted duration of study drug interruption).
- The investigator must complete and submit the Incyte Clinical Trial Pregnancy Form to the sponsor or its designee within **24 hours** of learning of the pregnancy.

Data on fetal outcome are collected for regulatory reporting and drug safety evaluation. Follow-up should be conducted for each pregnancy to determine outcome, including spontaneous or voluntary termination, details of the birth, and the presence or absence of any birth defects, congenital abnormalities, or maternal and/or newborn complications, by following until the first well-baby visit. Pregnancy should be recorded on a Clinical Trial Pregnancy Form and reported by the investigator to the sponsor or its designee. Pregnancy follow-up information should be recorded on the same form and should include an assessment of the possible causal relationship to the sponsor's study drug to any pregnancy outcome, as well as follow-up to the first well-baby visit or the duration specified in local regulations, whichever is later. Refer to the Incyte Reference Guide for Completing the Clinical Trial Pregnancy Form or Study Reference Manual.

Any SAE occurring during pregnancy of a study participant must be recorded on the Serious Adverse Event Report Form and submitted to the sponsor or its designee.

Abnormal pregnancy outcomes (eg, spontaneous abortion, fetal death, stillbirth, congenital anomalies, or ectopic pregnancy) are considered SAEs (if occurring in the study participant) and must be reported as described in Section 9.4. If an abnormal pregnancy outcome is reported in a study participant's partner, the event should be reported to the sponsor on the Clinical Trial Pregnancy Form.

9.8. Warnings and Precautions

Special warnings or precautions for the study drug, derived from safety information collected by the sponsor or its designee, are presented in the IB. Additional safety information collected between IB updates will be communicated in the form of Investigator Notifications. Any important new safety information should be discussed with the participant during the study as necessary. If new significant risks are identified, they will be added to the ICF.

9.9. Product Complaints

The sponsor collects product complaints on study drugs and drug delivery systems used in clinical studies in order to ensure the safety of study participants, monitor quality, and facilitate process and product improvements.

All product complaints associated with material packaged, labeled, and released by the sponsor or its designee will be reported to the sponsor. All product complaints associated with other study material will be reported directly to the respective manufacturer.

The investigator or his/her designee is responsible for reporting a complete description of the product complaint via email or other written communication to the sponsor contact or respective manufacturer as noted in the packaging information. Any AE associated with a product complaint should be recorded as described in Section 9.3.

If the investigator is asked to return the product for investigation, he/she will return a copy of the product complaint communication with the product.

9.10. Treatment of Overdose

There has been no clinical experience with overdose of INCB054707. Treatment of overdose should consist of general supportive measures.

10. STATISTICS

10.1. Sample Size Determination

In order to provide a safety database and adequate power for efficacy analysis, the total sample size for the study is 140 participants randomized in a 1:1:1:1 ratio to INCB054707 15 mg, 45 mg, or 75 mg or placebo groups. The sample size calculation is based on Fisher exact test for the statistical comparison on the primary efficacy endpoint, proportion of participants achieving \geq 4-point improvement in Itch NRS score at Week 16. Based on the result from a Phase 2 trial of nemolizumab (Ständer et al 2020), the response rate is assumed to be 50% for the INCB054707 45 mg or 75 mg groups and 15% for the placebo group. Using a 2-sided alpha of 0.05, 35 participants per group will have 85% power to detect such a difference between either 1 of the 3 active treatment groups and the placebo group.

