10.4.1. Primary Analysis

The primary analysis will be based on the ITT population. The primary alternative hypothesis (superiority of the INCB054707 groups compared with the placebo group for the proportion of participants achieving \geq 4-point improvement in Itch NRS score at Week 16) will be tested using exact logistic regression (Mehta and Patel 1995). This model will include the treatment groups and stratification factor. The unadjusted p-values between each of the INCB054707 groups and the placebo group will be compared with the prespecified significance level. Odds ratio and corresponding 95% CI will be provided as well. All nonresponders in the placebo-controlled period, as well as all participants who are missing postbaseline values, will be defined as nonresponders for the nonresponder imputation analysis. All participants who receive rescue therapy during the placebo-controlled period will be imputed as nonresponders.

The endpoint of different active doses versus placebo will be tested in a fixed sequence from high to low (75 mg, 45 mg, and 15 mg) at 2 sided $\alpha = 0.5$ level. The lower dose will be tested only if the statistical hypothesis associated with the higher dose is rejected.

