3.2. Control of Type I Error

The overall significance level for efficacy analysis will be 0.05 for 2-sided tests.

A set of hypotheses corresponding to the treatment comparisons between povorcitinib 15, 45, or 75 mg and placebo will be tested in fixed sequential:

- H1: Povorcitinib 75 mg is not equal to placebo in achieving ≥ 4-point improvement in Itch NRS score at Week 16
- H2: Povorcitinib 45 mg is not equal to placebo in achieving ≥ 4-point improvement in Itch NRS score at Week 16
- H3: Povorcitinib 15 mg is not equal to placebo in achieving ≥ 4-point improvement in Itch NRS score at Week 16

Hypothesis 2 will only be tested if H1 is rejected; testing for H3 will be implemented only if H1 and H2 are rejected.

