3.3. Sample Size Considerations

In order to provide a safety database and adequate power for efficacy analysis, the total sample size for the study is 140 participants randomized in a 1:1:1:1 ratio to povorcitinib 15, 45, or 75 mg or placebo groups and stratified by IGA score on Day 1 (3 vs 4). The sample size calculation is based on Fisher's exact test for the statistical comparison on the primary efficacy endpoint, ie, the proportion of participants achieving \geq 4-point improvement in Itch NRS at Week 16. Based on the results from a Phase 2 trial of nemolizumab (Stander et al 2020), the response rate is assumed to be 50% for the povorcitinib 45 and 75 mg groups and 15% for the placebo group. Using a 2-sided alpha of 0.05, 35 participants per group will have 85% power to detect such a difference between either one of the 3 active treatment groups and the placebo group.

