7.3. Efficacy Hypotheses

The primary hypothesis is that povorcitinib 75 mg is superior to placebo in proportion of participants achieving \geq 4-point improvement in Itch NRS at Week 16. If the response rates of achieving \geq 4-point improvement in Itch NRS at Week 16 in the povorcitinib 75 mg and placebo groups are denoted as p_T and p_C , respectively, then the primary hypotheses of the study are as follows:

- H_0 (null hypothesis): $p_T = p_C$
- H_A (alternative hypothesis): $p_T \neq p_C$

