7.4.1. Primary Efficacy Analysis

The primary efficacy analysis will compare povorcitinib 75 mg versus placebo in the proportion of participants achieving \geq 4-point improvement in Itch NRS score at Week 16 using an exact logistic regression (Mehta and Patel 1995) based on the ITT population. This model will include the treatment groups (placebo and povorcitinib 15, 45, and 75 mg) and stratification factor (Day 1 IGA score [3 or 4]). The unadjusted p-values between each of the povorcitinib groups and the placebo group will be compared at 2-sided $\alpha = 0.05$ in a fixed sequence from high dose to low dose (75 mg vs placebo \rightarrow 45 mg vs placebo \rightarrow 15 mg vs placebo); the lower dose will be tested only if the null hypothesis associated with the higher dose is rejected. The estimated odds ratios and corresponding 95% CIs will be provided as well. All observed nonresponders, as well as all participants who discontinue study treatment, withdraw from the study for any reason at any time before the timepoint of interest (ie, Week 16), or those participants that do not have the postbaseline assessment at the timepoint of interest, will be defined as nonresponders for the NRI analysis. All participants who receive rescue therapy during the placebo-controlled period will be imputed as nonresponders for all subsequent visits after the initiation date of rescue therapy.

The number of participants achieving \geq 4-point improvement in Itch NRS score at Week 16 and the respective rates, as well as the 2-sided 95% exact CIs, which are based on the Clopper-Pearson method, will be presented by treatment group.

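### The stated 85% power is a correct single-comparison figure, but under the fixed sequence 45 mg has about 76%, and 15 mg has no assumed response rate at all

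*Protocol*

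**What the plan says.** Protocol 10.1 bases the sample size on a Fisher exact test of the Week 16 itch response. "Using a 2-sided alpha of 0.05, 35 participants per group will have 85% power", and the claim is worded as follows: "35 participants per group will have 85% power to detect such a difference between either 1 of the 3 active treatment groups" and placebo. SAP 3.3 repeats it: "35 participants per group will have 85% power to detect such a difference between either one of the 3 active treatment groups" and placebo.

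The rates behind it cover two active doses only. In SAP 3.3, "the response rate is assumed to be 50% for the povorcitinib 45 and 75 mg groups and 15% for the placebo group". Protocol 10.1 gives the same rates. Neither section gives a rate for 15 mg, and neither mentions the order of testing.

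That order is set elsewhere. Protocol 10.4.1 runs from 75 to 45 to 15 mg: "The lower dose will be tested only if the statistical hypothesis associated with the higher dose is rejected". SAP 3.2 agrees: "Hypothesis 2 will only be tested if H1 is rejected; testing for H3 will be implemented only if H1 and H2 are rejected". SAP 7.3 and 7.4.1 name 75 mg against placebo as the primary comparison: "The primary efficacy analysis will compare povorcitinib 75 mg versus placebo in the proportion of participants achieving" the itch response.

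**The concern.** The sample-size sections and the testing sections do not describe the same thing, in two respects.

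- **Scope of the assumption.** Rates are assumed for two active doses, but power is stated for three. The 15 mg figure has no stated basis.
- **Scope of the test.** The 85% belongs to one comparison taken alone. Under the sequence, declaring 45 mg requires two tests to succeed and declaring 15 mg requires three. Their power cannot exceed the single-test figure and will normally be lower.

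Protocol 2.3.1 describes the trial as proof of concept and dose ranging, so what can be concluded for the lower doses is part of its purpose. A reader who takes 85% as the power for each dose would read too much into a 45 or 15 mg comparison that is not significant or is never reached. Only formal conclusions are affected: under SAP 7.4.1, response rates and odds ratios with confidence intervals are provided whatever the sequence shows.

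**Working it through.** **Inputs**

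- 35 per group; 140 in total, 1:1:1:1 (Protocol 10.1, SAP 3.3).
- Fisher exact test, 2-sided 0.05 (Protocol 10.1, SAP 3.3). Protocol 10.4.1 prints the step level as 0.5. Protocol 10.3 and SAP 7.4.1 have 0.05, which is used here.
- Response rates: placebo 15%, 45 mg 50%, 75 mg 50%; none for 15 mg (both sample-size sections).
- Sequence 75, 45, 15 mg, with one placebo arm used in every comparison (Protocol 10.4.1, SAP 3.2 and 7.4.1).

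**Formula**

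Let c be the number of placebo responders, c ~ Bin(35, 0.15). For an active arm with true rate q, let r(c, q) be the probability, over t ~ Bin(35, q), that the 2-sided Fisher p-value for t/35 against c/35 is at most 0.05. Given c, the active arms are independent, so:

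- single comparison: Σ P(c) · r(c, q)
- 45 mg under the sequence: Σ P(c) · r(c, q75) · r(c, q45)
- 15 mg under the sequence: Σ P(c) · r(c, q75) · r(c, q45) · r(c, q15)

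Summing over c accounts for the shared placebo arm.

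**Step 1: the plan's own figure.** With q = 0.50, the single comparison gives 0.8522. The stated 85% reproduces.

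**Step 2: 45 mg under the sequence.** With q75 = q45 = 0.50, the sum is 0.7561; 400,000 simulated trials also gave 0.756. If the two tests were independent it would be 0.8522² = 0.726, so sharing the placebo arm recovers about three points. The chance of not declaring 45 mg is 1 − 0.756 = 24%, against 1 − 0.852 = 15% for a stand-alone test.

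**Step 3: 15 mg.** The documents supply no rate, so the first column is assumed. The 75 and 45 mg rates stay at 50%.

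| Assumed 15 mg rate | Power under the sequence |
|---|---|
| 20% | 4% |
| 25% | 11% |
| 30% | 22% |
| 40% | 49% |
| 50% | 68.5% |

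Taken alone, outside the sequence, 15 mg would have 23% power at a 30% rate, 56% at 40% and 85.2% at 50%.

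**Step 4: dependence on the 75 mg rate.** With 45 mg held at 50%, its power under the sequence varies with the true 75 mg rate:

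| True 75 mg rate | Power for 45 mg under the sequence |
|---|---|
| 45% | 66% |
| 50% | 76% |
| 55% | 81% |
| 60% | 84% |
| 65% | 85% |

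**For scale only.** At 50% for both doses, 41 per group gives 84.2% for 45 mg under the sequence and 42 gives 85.6%. That is 4 × 42 = 168 in total against the planned 140. No increase is proposed.

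**The case against.** The best defence is that the sentence is conditional and pairwise. It refers to detecting a particular difference, 50% against 15%, in one comparison with placebo. Read that way it is true of any arm of 35, including 15 mg, and it does not promise that each dose will be declared with that probability. Pairwise power does not in itself contradict a fixed sequence, the named primary comparison is the first step, and SAP 3.2 sets out the sequence immediately before SAP 3.3. On this view the plan is incomplete rather than wrong.

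Part of this stands. The 85% is correct for 75 mg, and for any dose with a 50% rate tested alone. But the lower doses are not tested alone. Even on the conditional reading, the planned procedure gives 75.6% for 45 mg and 68.5% for a 15 mg dose as good as the others. The sentence names three doses, and for two of them the design does not have the stated power.

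Two further points are fair. The 76% depends on the true 75 mg rate, and the shortfall largely disappears if 75 mg does clearly better than 50%. Any restated figure must therefore carry its condition. Also, the planned analysis is exact logistic regression with the IGA stratum, not Fisher. Fisher is used here because both sample-size sections name it. An approximate check with a pairwise stratified exact test, assuming equal rates in both strata and IGA splits of 50–80%, gave about 75–76% for 45 mg, so the choice of test does not explain the gap.

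**Conclusion.** The concern holds. The 85% is the right number attached to too wide a claim. On the sponsor's assumptions (50% on both higher doses, 15% on placebo, 35 per group, Fisher at 2-sided 0.05, shared placebo), power is 85.2% for 75 mg and 75.6% for 45 mg under the fixed sequence. For 15 mg no power under the sequence follows from the documents, because no rate is assumed; 68.5% would need a 15 mg rate equal to the higher doses. The sample size and the power for the primary comparison are not in question. This should be corrected, but it does not threaten the primary analysis.

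**What to change.** Restate the power in Protocol 10.1 and SAP 3.3 along these lines:

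> About 85% power for 75 mg versus placebo (single comparison, 50% versus 15%); about 76% for 45 mg under the fixed sequence if both doses have a 50% response rate; no response rate is assumed for 15 mg, and the study is not powered for that comparison.

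Nothing else changes: sample size, test, alpha and planned estimates stay as they are. The cost is one sentence in each document and a less favourable stated figure for the two lower doses. Because Protocol 11.1 requires approval of amendments by health authorities and the IRB/IEC, the protocol sentence can wait for the next amendment; the SAP sentence can be changed at its next revision.

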10.2. Populations for Analysis

The populations for analysis are provided in Table 13.

Population	Description
ITT	The ITT population includes all randomized participants. Treatment groups for this population will be defined according to the treatment assignment at randomization.
Safety	The safety population includes all participants who received at least 1 dose of study drug. Treatment groups for this population will be determined according to the actual treatment the participant received on Day 1.

Table 13:Populations for Analysis

10.3. Level of Significance

The overall significance level for efficacy analysis will be 0.05 for 2-sided tests.

10.4. Statistical Analyses

The SAP will be developed and finalized before database lock and will describe the participant populations to be included in the analyses and procedures for accounting for missing, unused, and spurious data. This section is a summary of the planned statistical analyses of the primary and secondary endpoints.

10.4.1. Primary Analysis

The primary analysis will be based on the ITT population. The primary alternative hypothesis (superiority of the INCB054707 groups compared with the placebo group for the proportion of participants achieving \geq 4-point improvement in Itch NRS score at Week 16) will be tested using exact logistic regression (Mehta and Patel 1995). This model will include the treatment groups and stratification factor. The unadjusted p-values between each of the INCB054707 groups and the placebo group will be compared with the prespecified significance level. Odds ratio and corresponding 95% CI will be provided as well. All nonresponders in the placebo-controlled period, as well as all participants who are missing postbaseline values, will be defined as nonresponders for the nonresponder imputation analysis. All participants who receive rescue therapy during the placebo-controlled period will be imputed as nonresponders.

The endpoint of different active doses versus placebo will be tested in a fixed sequence from high to low (75 mg, 45 mg, and 15 mg) at 2 sided $\alpha = 0.5$ level. The lower dose will be tested only if the statistical hypothesis associated with the higher dose is rejected.

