Description of change: Updated the level of significance wording and revised the 2 sided $\alpha = 0.049$ level to 2 sided $\alpha = 0.5$ in alignment with removal of the interim analysis section.

Rationale for change: To align with removal of the interim analysis.

13. Section 10.5, Interim Analysis

Description of change: Removed interim analysis.

Rationale for change: An interim analysis is not needed due to emerging safety and efficacy data for INCB054707 in other indications.

14. **Incorporation of administrative changes:** Other minor administrative changes have been incorporated throughout the Protocol and are noted in the redline version of the amendment.

Amendment 1 (12 JUL 2021)

Overall Rationale for the Amendment:

The primary purpose of the amendment is to change the inclusion criteria associated with minimum number of nodules, to include a substudy for itch and sleep monitoring assessment, and to revise the interim analysis. Additional changes are summarized below.

 Section 1, Protocol Summary (Table 2: Key Study Design Elements; Figure 1: Study Design Schema); Section 4.1, Overall Design; Section 5.1, Inclusion Criteria

Description of change: Changed the inclusion criteria for minimum number of nodules from 10 to 20.

Rationale for change: To align the minimum nodule count with the range listed in the description of Grade 3 in Table 11.

2. Section 1, Protocol Summary, (Table 2: Key Study Design Elements)

Description of change: Added the name for the coordinating principal investigator.

Rationale for change: To update the coordinating principal investigator field in the table.

3. Section 1, Protocol Summary (Table 3: Schedule of Activities for the Placebo-Controlled Period

Description of change:

Rationale for change:

4. Section 1, Protocol Summary (Table 3: Schedule of Activities for the Placebo-Controlled Period

Description of change: Added Follow-up phone call (eDiary compliance) to the table.

Rationale for change: To coincide with the text in Section 8.3.1 of the Protocol.

5. Section 3, Objectives and Endpoints (Table 6: Objectives and Endpoints)

Description of change:

Rationale for change:

VV-CLIN-013854

6. Section 5.2, Exclusion Criteria (Table 7: Exclusionary Laboratory Values)

Description of change: Removed "Conjugated (direct) bilirubin" and $\geq 1.2 \times ULN$ from Exclusion Criterion 16g.

Rationale for change: To clarify that Exclusion Criterion 16g is only applicable to total bilirubin.

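### Protocol 10.4.1 sets the primary dose comparisons at a two-sided alpha of 0.5, where the rest of the protocol and the SAP use 0.05

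*Protocol*

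**What the plan says.** Protocol 10.4.1 is the section that defines the primary test. It orders the dose comparisons "from high to low (75 mg, 45 mg, and 15 mg) at 2 sided $\alpha = 0.5$ level", and each lower dose is tested only after the higher one succeeds. The same section attaches 95% confidence intervals to the odds ratios from these tests.

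Every other statement of the level is a two-sided 0.05:

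- Protocol 10.1: "Using a 2-sided alpha of 0.05, 35 participants per group will have 85% power to detect such a difference".
- Protocol 10.3: "The overall significance level for efficacy analysis will be 0.05 for 2-sided tests". SAP 3.2 repeats this sentence.
- SAP 3.3 repeats the sample size statement, including the 0.05.
- SAP 7.4.1, for the same 75, 45, 15 mg sequence: the p-values "will be compared at 2-sided $\alpha = 0.05$ in a fixed sequence from high dose to low dose".

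Protocol Appendix F (Amendment 2, item 12) records that the level in 10.4.1 was changed from 0.049 to 0.5 to fit the removal of the interim analysis. SAP 2.1 states that the SAP is based on Amendment 2, and SAP 11.1 lists no changes to protocol-defined analyses.

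**The concern.** The figure in 10.4.1 is ten times the level used everywhere else, and it sits in the rule that decides the primary endpoint and opens the gate to each lower dose. It is in the current text. The amendment log gives the same 0.5, so it is not a fault of reading the PDF.

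Because SAP 7.4.1 gives 0.05, the analysis would be expected to run at 0.05. The problem is that the protocol and the SAP then disagree on the primary threshold, and SAP 11.1 says nothing about it. Someone reading the protocol alone would find a decision rule that gives almost no protection against a false positive.

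**Working it through.** **Inputs.** 35 participants per arm, Fisher's exact test for sizing, and response rates as in Protocol 10.1: "the response rate is assumed to be 50% for the INCB054707 45 mg or 75 mg groups and 15% for the placebo group". The alpha is 0.05 (Protocol 10.1, 10.3; SAP 3.2, 3.3, 7.4.1) or 0.5 (Protocol 10.4.1).

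**Method.** Let i and j be the responder counts on drug and placebo. Over all 36 × 36 outcomes,

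P(reject) = Σ Bin(i; 35, p_T) × Bin(j; 35, p_C) × 1{ p_F(i, j) ≤ alpha },

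where p_F is the two-sided Fisher p-value. It sums the hypergeometric probabilities C(35, k) C(35, i+j−k) / C(70, i+j) over all k whose probability is no larger than that of the observed table. Unequal rates give power, and equal rates give the type I error.

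**Step 1: the plan's own figure (p_T = 0.50, p_C = 0.15).**

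| Two-sided alpha | Power | Stated 85%? |
|---|---|---|
| 0.05 | 85.2% | reproduced |
| 0.049 (former level) | 85.2% | reproduced |
| 0.5 | 99.1% | not reproduced |

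The power rules out 0.5. It cannot separate 0.05 from 0.049, because Fisher's test is discrete and rejects the same tables here. What identifies 0.05 is the text of Protocol 10.1 and 10.3 and SAP 7.4.1.

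**Step 2: type I error of the first comparison (75 mg against placebo) if 10.4.1 were followed literally.**

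| Common true rate (only 15% is from the plan, as its placebo rate) | alpha 0.05 | alpha 0.5 |
|---|---|---|
| 10% | 1.3% | 30.3% |
| 15% | 2.2% | 31.1% |
| 20% | 2.5% | 31.2% |
| 25% | 2.6% | 33.5% |
| 30% | 2.8% | 36.1% |

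The values lie below the nominal alpha because the test is discrete. At 15%, counting only results that favour the drug halves them by symmetry: 2.16% / 2 = 1.1%, and 31.08% / 2 = 15.5%. When no dose works, a false claim requires the first test to reject, so these two-sided figures are also the family-wise error of the whole sequence. A simulation of the three steps with 400,000 runs at 15% agreed (2.2% and 31.1%).

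**Step 3: what would pass.** Suppose placebo has 5/35 responders.

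| Drug responders | Fisher p | Passes at 0.05 | Passes at 0.5 |
|---|---|---|---|
| 9/35 | 0.371 | no | yes |
| 13/35 | 0.054 | no | yes |
| 14/35 | 0.030 | yes | yes |

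**Step 4: a test closer to the planned model.** The planned analysis is exact logistic regression with the IGA stratum. A two-arm stratified exact conditional test was enumerated in full. Assumptions: 7, 14 or 17 of the 35 in each arm have IGA 4, and both strata share the same response rate.

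| IGA 4 per arm | Type I error at 15%, alpha 0.05 | Type I error at 15%, alpha 0.5 | Power, alpha 0.05 | Power, alpha 0.5 |
|---|---|---|---|---|
| 7 | 2.19% | 31.10% | 85.1% | 99.1% |
| 14 | 2.21% | 31.25% | 85.2% | 99.1% |
| 17 | 2.20% | 31.17% | 85.2% | 99.1% |

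The unstratified figures are therefore an adequate stand-in.

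**The case against.** The strongest case against giving this much weight is that the documents already leave little doubt. Protocol 10.3 sets the overall level at 0.05. Protocol 10.4.1 itself refers to a prespecified level and pairs the tests with 95% intervals. Protocol 10.4 calls the section a summary of the planned analyses, and SAP 7.4.1 gives 0.05 for the same sequence. The 31.1% arises only if someone follows 10.4.1 against all of these, and taking the documents as a whole the expected effect on the type I error is nil.

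Most of this stands. The error rates are conditional on a literal reading, and no changed analysis is expected. The stratified check is also not the full planned model, which fits all four arms.

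It does not remove the point. The wrong figure is in the current primary-analysis section, the protocol contradicts itself there, and SAP 11.1 records no departure. That the correct level can be inferred is a reason why the correction is easy, not a reason to leave it.

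**Conclusion.** The concern holds, with high confidence. Protocol 10.4.1 is wrong as written: it gives 0.5 where Protocol 10.1 and 10.3 and three SAP sections give 0.05. It should be corrected because it is the stated threshold for the primary endpoint and for the gate to each lower dose.

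In practice the consequence is a conflict between governing documents. Only on a literal reading does the false-positive rate of the first comparison rise from 2.2% to 31.1%. That figure assumes a common 15% response rate, 35 analysed per arm, and Fisher's test in place of the exact logistic regression. Common rates of 10% to 30% and the stratified check lead to the same conclusion.

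A separate and minor wording point: SAP 3.2 words H1 to H3 as alternatives (drug differs from placebo) and then speaks of rejecting them: "Hypothesis 2 will only be tested if H1 is rejected". SAP 7.3 states the null hypothesis correctly, and so does the gate in SAP 7.4.1: "the lower dose will be tested only if the null hypothesis associated with the higher dose is rejected". No result depends on this.

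**What to change.** Change the level in Protocol 10.4.1 to a two-sided alpha of 0.05. If the protocol is not amended, replace the entry in SAP 11.1 with one line that records the discrepancy and states that 0.05 is the level used. Only one of the two is needed.

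Neither changes the sample size, the power or the planned analysis. A protocol amendment needs Health Authority and IRB/IEC approval under Protocol 11.1, so that route is cheapest if another amendment is due anyway. Otherwise the SAP line is the lighter option.

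When the SAP is next edited, restate H1 to H3 in SAP 3.2 as null hypotheses (response rate equal to placebo), in line with SAP 7.3 and 7.4.1. This is a text change only.
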